Adherence of patients with type 2 DM to medication is associated with better balanced glycemic control (HbA1c <7%), thus helping in reduction of microvascular and macrovascular complications ^[6].

Adherence to medication is mainly influenced by several factors such as demographic, socioeconomic, cultural, health system related factors, educational and personal factors such as patient's age, complexity of medication, side effects, cost, availability, accessibility and whether they're receiving emotional and social support from their families [7].

Mental representation of DM affect patients' coping behavior. Many patients lack the understanding of type 2 DM. Perception of the disease is important, it's not just about taking the prescribed medication, it's about the extent to which the patient follows medical instructions [8].

Studies have showed that illness perception and beliefs about medication by type 2 DM patients is commonly linked with their adherence to medication and in return better glycemic control [9].

Perception is about everything regarding the illness such as illness identity, time line of the disease, consequences, comorbid conditions, number of hospital admission, whether it can be controlled or not, and emotional response to being diabetic [10]. Beliefs in self-control and self-management over health will affect adherence to treatment regimens and glycemic control [9].

Perception about illness shapes self-management behavior. If patients have strong perception about treatment plan and regimen with personal control, it'll lead to lower level of HbA1c and better health outcome [10].

Patients' beliefs about medication are mainly about the necessity of taking the prescribed medication to maintain their health now and in the future, and concerns about the possible negative effects of taking the medication such as addiction or long-term adverse effects from regular use. Some patients believe that medication helps them, while others believe that multiple harmful effects of the treatment may outweigh any positive outcomes. Some of the patients who have strong opinions about their medication avoid taking it or, conversely, abuse it [11].

Patients who are convinced that a specific medication is essential for their health are much more likely to adhere to the treatment than those who do not hold such a belief [12].

We hypothesize that some factors associated with non-adherence to medication can be investigated so that interventions can be implemented to increase adherence to medication, helping in achieving better glycemic control and better health outcomes and reducing complications.

As data concerning diabetic patients' adherence are deficient in upper Egypt, this study will help in filling the gap on illness perception and beliefs about medication, which in turn affects patients' adherence to medication and thus better glycemic control in type 2 DM.

Rationale

Data regarding predictors of adherence to diabetes medication is limited in Egypt. This study aims to investigate whether illness perception, beliefs about medication were associated with adherence to medication and glycemic control (HbA1c) in Egyptian patients with type 2 diabetes in Diabetes Clinic in Assiut University Hospital. To the best of our knowledge, no previous studies on adherence to medication were done in Assiut Governorate.

Objectives of the study

- 1- Assess medication adherence among diabetic patients attending Diabetes Clinic in Assiut University Hospital.
- 2- Identify patients' beliefs about medication and illness perception.
- 3- Link patient's beliefs about medication and illness perception with medication adherence.
- 4- Investigate the correlates of medication adherence, illness perception, and beliefs about medication.

Subjects and methods

Study Design and setting

The present study will be cross sectional. This study will be conducted in Assiut University Hospital. The target population will include diabetic patients attending Diabetes Clinic in Assiut University Hospital. The clinic offers various services including clinician consultations, health education, medication dispensing, foot, and vision screening. The clinic is also responsible for treating and monitoring patients with diabetes. All patients who fulfill the inclusion criteria and presented to Diabetes Clinic in Assiut University Hospital will be included in the present study

Sample size estimation

The sample size was calculated using the Epi info version 7 StatCalc, based on the following assumption: prevalence rate of non-adherence among Egyptian population (55.5%) [13], level of confidence 95%, precision 5%, and design effect 1. The calculated sample size was raised to 417 after adding 10% as non-response rate.

Inclusion criteria

- 1- Patients who are diagnosed with type 2 DM for at least 1 year according to the diagnostic criteria of the 10th revision of the International Classification of Diseases (ICD-10).
- 2- Patients treated with insulin or oral medication or both for at least 6 months.
- 3- Age group: adult patients (> 18 years old) will be included in the present study.

Exclusion criteria

- 1- Newly diagnosed diabetic patients or ill on the day of recruitment, or not taking any medications for type2 DM
- 2- Patients with type1 DM
- 3- Psychiatric patients or on anti-depressant treatment or using psychotropic drugs affecting their cognitive ability.

Data collection tool

Data will be collected through semi-structured questionnaires which will be filled by the researcher herself. The questionnaire will be composed of five parts:

- The first part will inquire about sociodemographic data such as age, sex, educational level, occupation, residence, and marital status.
- The second part is about clinical data including BMI, duration of diabetes, type and number of prescribed medications, number of comorbid conditions, number of diabetes-related complications, and patients' most recent HbA1c levels were taken from medical records. HbA1c levels of $\geq 8\%$ indicate suboptimal glycemic control in patients with T2D.
- The third part of the questionnaire is the Arabic version of Morisky Medication Adherence Scale (MMAS-8) [14]. It remains one of the most widely used mechanisms to assess patient adherence [14]. It consists of 8 questions.

Response choices are "yes" or "no" for items 1 through 7 and Item 8 has a five-point Likert response scale. Each "no" response is rated as 1 and each "yes" response is rated as 0 except for item 5, in which each "yes" response is rated as 1 and each "no" response is rated as 0. For Item 8, the code (0-4) must be standardized by dividing the result by 4 to calculate a summated score [14]. Total scores on the MMAS-8 range from 0 to 8, with scores of 8 reflecting high adherence, 7 or 6 reflecting medium adherence, and <6 reflecting low adherence [14].

The fourth part of the questionnaire is the Brief Illness Perception Questionnaire (B-IPQ). B-IPQ is a rapid assessment tool with a Cronbach's alpha of 0.65 that measures eight different aspects of illness perception: consequences, timeline, personal control, treatment control, identity, concerns, understanding, and emotional representation [15]. The B-IPQ is a 9-item instrument that measures illness perception from eight different aspects using an 11-point Likert scale. A higher score reflects a more threatening view of the illness, while a lower score indicates a benign view of the illness [15]

The fifth part of the questionnaire is the Beliefs about medicine which is assessed using the Arabic version of the Beliefs about Medicines Questionnaire Specific (BMQ-Specific). It includes two subscales, which evaluate patients' perceptions of the necessity of medicine in controlling their illness (Necessity-Specific) and concerns about potential adverse effects of medicine (Concerns-Specific). Each subscale consists of 5 items and is scored on a 5-point Likert scale. High scores on the Necessity-Specific subscale indicate that the patient perceives their medicine as necessary, whereas high scores on the Concerns-Specific subscale indicate that the patient is concerned about potential adverse effects [16].

Statistical analysis

Data entry and analysis will be carried out using SPSS version 24. Descriptive statistics will be done in the form of frequencies, mean and SD then analytic statistics will be done as chi square, independent sample test and correlations tests. Values will be considered significant when P values are equal to or less than 0.05.

Pilot study

Before starting to collect data, a pilot study will be carried out to fulfill the following purposes:

- 1- Testing the questionnaire form and detecting any modification required.
- 2- Estimation of the time needed to fill the questionnaire.
- 3- Detection of the difficulties that may arise and how to deal with them.

Ethical Considerations

- 1- The research proposal will be reviewed and approved by the Ethical Committee of Assiut Faculty of Medicine.
- 2- Administrative permission will be obtained from the University authority.
- 3- Informed written consent will be obtained from subjects before being included in the study.
- 4- Privacy and confidentiality of the data will be assured.

References:

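### Does the B-IPQ score cancel itself out because no reversal is written down for the control and understanding aspects?

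*Combined protocol and SAP*

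**What the plan says.** The B-IPQ is the fourth part of the questionnaire (Data collection tool). Its aspects are listed as "consequences, timeline, personal control, treatment control, identity, concerns, understanding, and emotional representation". On format the plan says "The B-IPQ is a 9-item instrument that measures illness perception from eight different aspects using an 11-point Likert scale", and on reliability "B-IPQ is a rapid assessment tool with a Cronbach's alpha of 0.65". The direction of scoring is one sentence for the whole instrument: "A higher score reflects a more threatening view of the illness, while a lower score indicates a benign view of the illness". The instrument paper, reference 15, is cited for the aspects and for the direction.

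The plan does not give the item coding, any reversal, whether a total or separate aspect scores are analysed, or how nine items map to eight aspects. The Statistical analysis section names chi-square, independent-sample and correlation tests and adds no scoring rule.

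The background text treats control as favourable: "If patients have strong perception about treatment plan and regimen with personal control, it'll lead to lower level of HbA1c and better health outcome".

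**The concern.** An aspect called personal control, treatment control or understanding would naturally score higher when the patient has more of it. The background presents these as good things. On raw scores, the single stated direction would then be wrong for three aspects out of eight. A raw sum would add five aspects keyed towards threat to three keyed away from it.

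The omission stands out because the third part of the questionnaire spells out the one reverse-scored MMAS-8 item (item 5), the rescaling of item 8 and the cut-offs.

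Illness perception enters objectives 2, 3 and 4. If its score mixed opposite meanings, its mean could not be read as threatening or benign. Its association with adherence could also be diluted enough to be missed.

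**Working it through.** **Sample size, to see whether it is touched.** Inputs from Sample size estimation: p = 0.555, precision 0.05, 95% confidence, 10% added.

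- n = 1.96² × 0.555 × 0.445 / 0.05² = 379.5
- 379 × 1.10 = 416.9, so 417

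The plan's figure reproduces. It rests on the prevalence of non-adherence only, so B-IPQ scoring cannot affect it.

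**What an unreversed sum would do.** Assumptions: eight items of equal variance, one common factor, and the same absolute correlation r between items. Five items are keyed towards threat and three away from it. The only input from the plan is alpha = 0.65.

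- From alpha = 8r/(1 + 7r): r = 0.65/(8 − 0.65 × 7) = 0.65/3.45 = 0.188, so the loading is √0.188 = 0.434.
- Let s be the net number of items pulling the same way: 8 if reversed, 5 − 3 = 2 if not. The variance of the sum is 8 + r(s² − 8).
- Reversed: variance 8 + 56r = 18.55; correlation with the factor 8 × 0.434/√18.55 = 0.81.
- Unreversed: variance 8 − 4r = 7.25; correlation with the factor 2 × 0.434/√7.25 = 0.32.
- Ratio: 0.322/0.806 = 0.40.

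| alpha | r | ratio, unreversed to reversed | alpha of the unreversed sum |
|---|---|---|---|
| 0.50 | 0.111 | 0.34 | −0.07 |
| 0.65 | 0.188 | 0.40 | −0.12 |
| 0.80 | 0.333 | 0.50 | −0.23 |

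As an illustration, a correlation of 0.20 with adherence would become 0.20 × 0.40 = 0.08. By Fisher's z at n = 379 and two-sided 0.05, power would fall from 98% to 34%. If items are coded 0 to 10 (not stated), the most threatening and most benign profiles score 80 and 0 when reversed. Unreversed they score 5 × 10 = 50 and 3 × 10 = 30, so the span shrinks from 80 to 20.

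**Which scoring fits the plan's own statements.** The alpha of an unreversed sum is (8/7) × (1 − 8/(8 − 4r)). This is negative for every positive r, and −0.12 at r = 0.188. An instrument described as having an alpha of 0.65 is therefore not, under this model, a raw sum with three items pointing the other way. The stated direction leads to the same place, because a total rises with threat across all eight aspects only when the three favourable ones have been reversed. No statement in the plan points to a raw sum.

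**How far the loss depends on the model.** The 0.40 ratio also needs adherence to relate to the items only through the single factor. Suppose instead that all eight raw items had the same positive covariance c with adherence. The reversed total would then have covariance 5c − 3c = 2c and the raw total 8c, so the larger covariance would belong to the raw sum. The documents do not say which pattern holds.

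**The case for a change.** The strongest case for a change is that the plan should not leave a main explanatory variable to inference. It writes out the MMAS-8 scoring in full and leaves the B-IPQ, with more reverse-direction content, to a citation. Analysing the aspects singly does not rescue the sentence either: nothing cancels, but a high raw score on the three favourable aspects would still be described as threatening. One or two sentences would close the gap at almost no cost.

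Part of this stands. The scoring detail is absent, and the arithmetic for a raw sum is correct under its assumptions. But the harm needs a step that the plan does not contain, namely summing raw items against its own stated direction. Silence is not evidence of that step. The BMQ-Specific, the fifth part of the questionnaire, is also described only by its subscales, the direction of scoring and a citation, so the fully written MMAS-8 is the exception. On the single-aspect reading, the aspect names tell the analyst what a high raw score means.

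The wording suggested for the plan also goes beyond the documents. Reversing by 10 minus the score assumes 0 to 10 coding. Leaving the ninth item out of the sum assumes that it belongs to no aspect, which the plan does not say. Testing all eight aspects separately against MMAS-8 is a preference, and it would add multiplicity that the plan has no provision for.

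**Conclusion.** The concern does not call for a change. The plan omits the item coding, the reversal, the choice between total and aspect scores, and the place of the ninth item. An analyst who follows the cited instrument in the stated direction would get a score that means what the plan says it means.

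The loss to about 0.40 of the reversed correlation (0.34 to 0.50) describes an error the plan does not commit. It rests on equal inter-item correlations and a single factor, for a tool said to cover eight different aspects. That the three aspects run opposite to threat is itself inferred from their names and the background text, since the item wording is not in the documents.

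Provided item responses are entered singly, reversal is a recode available at any point before analysis. No data collection, estimate of adherence or sample size hangs on it.

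### Must the plan say whether illness perception is tested as one B-IPQ total or as eight separate aspects?

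*Combined protocol and SAP*

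**What the plan says.** In the Data collection tool section, the fourth part of the questionnaire is introduced thus: "The B-IPQ is a 9-item instrument that measures illness perception from eight different aspects using an 11-point Likert scale". The aspects are listed as "consequences, timeline, personal control, treatment control, identity, concerns, understanding, and emotional representation". One Cronbach's alpha, 0.65, is given for the tool. One direction is given: "A higher score reflects a more threatening view of the illness, while a lower score indicates a benign view of the illness". There is no summation rule, score range or item orientation, and nothing on how the ninth item is used.

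The other two scales are described more fully. For the adherence scale, item coding is written out, including the reversed item, and "Total scores on the MMAS-8 range from 0 to 8". For the beliefs questionnaire, two subscales of five items are named, each with its own direction.

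The Statistical analysis section lists chi-square tests, two-sample tests and correlations, without assigning variables to them. On the threshold it says: "Values will be considered significant when P values are equal to or less than 0.05". It names no main variable and no adjustment for multiple tests. Objective 3 links illness perception and beliefs with adherence. The Rationale is wider, asking "whether illness perception, beliefs about medication were associated with adherence to medication and glycemic control (HbA1c").

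**The concern.** Illness perception is one of the study's two main exposures, and the text could be read in two ways. Under one reading a single total is correlated with adherence. Under the other, eight aspects are each correlated with it. At an unadjusted 0.05 per test these carry very different risks of a chance finding, and nothing in the statistics section says which was intended. An analyst could choose after seeing the data, and a reader of the report could not tell.

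A second worry concerns the score itself. The introductory background treats "strong perception about treatment plan and regimen with personal control" as favourable, so at least that aspect appears to run opposite to threat. If a total is formed, its meaning depends on an orientation step that the plan does not write down.

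**Working it through.** **The plan's own figure.** Sample size estimation gives 417 from a prevalence of 55.5%, 95% confidence, 5% precision, design effect 1 and 10% added for non-response.

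- n = 1.96² × 0.555 × 0.445 / 0.05² = 379.5
- 379.5 × 1.10 = 417.5, which agrees with 417

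This calculation concerns the precision of a prevalence. It does not depend on how the B-IPQ is scored.

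**False-positive risk per outcome.** The inputs from the plan are a 0.05 level per test (taken as two-sided), eight aspects and alpha 0.65. The assumptions are that no aspect is associated with the outcome, that each aspect is tested once, and that the aspects are equally correlated.

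- One total: 5%.
- Eight independent tests: 1 − 0.95⁸ = 0.337.
- Mean item correlation implied by alpha 0.65 with eight items: r = 0.65 / (8 − 7 × 0.65) = 0.65 / 3.45 = 0.188.
- Eight tests with common correlation r: 1 − ∫ φ(u) [Φ((1.96 − √r·u)/√(1−r)) − Φ((−1.96 − √r·u)/√(1−r))]⁸ du. At r = 0.188 this is 0.321.
- A simulation of correlation tests with n = 379 and 8,000 runs gave 0.323 for the eight aspects and 0.053 for the total.
- With alpha 0.5, r = 0.5 / 4.5 = 0.111 and the risk is about 33%. With alpha 0.9, r = 0.9 / 1.7 = 0.529 and it is about 24%.

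The two routes therefore differ as feared: 5% against 24–34%.

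**What adjustment would cost.** Take n = 375 (417 less 10%), 80% power and Fisher's z, whose standard error is 1/√372 = 0.0518.

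- At 0.05: (1.960 + 0.842) × 0.0518 = 0.145, so r = 0.144.
- At 0.05/8 = 0.00625: (2.734 + 0.842) × 0.0518 = 0.185, so r = 0.183.

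The second value is an upper bound for Holm's procedure. At 0.00625 per test, the risk of any false positive among the eight falls to 4.8–4.9%.

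**Which route the text describes.** Three features of the Data collection tool section point to a total.

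1. One alpha is quoted for the instrument. Internal consistency is a property of items combined into a score, not of eight aspects kept apart.
2. One direction is given for the instrument. Where the plan means separate scores, as for the beliefs questionnaire, it names the subscales and gives a direction for each.
3. That direction would not hold for a raw personal-control rating if a high rating means more control, which the background regards as good. The sentence makes sense for a score already turned towards threat.

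The third feature also bears on orientation. A total summed without reversing favourable items would contradict the plan's own statement of what a high score means. Raw summing would be an error in carrying out the plan, not a choice that the plan leaves open.

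**The case for a change.** The strongest reply is that a leaning is not a specification. The aspects are listed one by one, either analysis would be consistent with the text, and the choice can be shown to be prespecified only if it is written down before the data are seen. The plan writes out the adherence scoring although it cites a source for that scale too, so brevity does not fully explain the omission. A citation may settle how items are scored, but it cannot say which variable this study tests. Nor does the plan call its tests exploratory.

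Much of this stands. The main variable is not named, and one sentence would name it. It does not follow that the planned analysis is unsound. The 24–34% applies only if every aspect is tested, every result is read at 0.05, and no aspect is associated with the outcome. The plan does not say the first, and its background cites studies in which illness perception is commonly linked with adherence, so the last is not the study's premise. The absence of adjustment is also not special to the B-IPQ: the same rule covers the beliefs subscales and all sociodemographic and clinical correlates. HbA1c as a second outcome appears in the Rationale but in none of the four objectives, so it gives weak support for a larger count of planned tests.

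Which items are reversed, and what becomes of the ninth, depends on the cited source, which cannot be examined here. Little can be built on those details either way.

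**Conclusion.** No change follows. The omission is missing detail, and the plan's description of the instrument supplies the sensible reading: one total, oriented so that higher means more threatening, tested at 5% per outcome. An analyst who follows it has a sound test.

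The alternative figure, about 32% with a range of 24–34%, is correct under its assumptions: eight unadjusted two-sided tests, equal item correlation (alpha 0.5–0.9, or independence at the upper end) and no true association. It describes a route that the plan does not state.

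The only step that would alter a result is adjusting the eight aspects, and that is a fair trade-off. It would restore the error rate to about 5% while raising the detectable correlation from 0.144 to at most 0.183. Reporting all eight with confidence intervals as exploratory would be equally defensible in a cross-sectional study sized for a prevalence. Reasonable statisticians differ on this, and neither choice affects the sample size of 417.

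### Only unadjusted tests are planned, so the study can show that beliefs and illness perception go with adherence, but not whether this holds among patients alike in the other factors it collects

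*Combined protocol and SAP*

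**What the plan says.** After descriptive statistics, the Statistical analysis section gives the whole inferential plan in one clause: "analytic statistics will be done as chi square, independent sample test and correlations tests", with significance at P of 0.05 or less. It names no covariate, regression, stratification or matching. The correlation tests could include partial correlation, but the plan does not say so.

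Other parts of the protocol bear on this:

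- **Influences on adherence (introduction):** "Adherence to medication is mainly influenced by several factors such as demographic, socioeconomic, cultural, health system related factors, educational and personal factors". The examples that follow include age and complexity of medication.
- **Data collection tool:** age, sex, education, occupation, residence, marital status, BMI, duration of diabetes, type and number of medicines, and numbers of comorbidities and complications are all recorded.
- **Objectives 3 and 4, and the aim in the Rationale:** the wording is that of linking, correlates and association. The aim also covers HbA1c.
- **Purpose (hypothesis paragraph):** "some factors associated with non-adherence to medication can be investigated so that interventions can be implemented to increase adherence to medication".
- **Directional wording:** the introduction describes perception and beliefs as something "which in turn affects patients' adherence to medication and thus better glycemic control". The Rationale opens with "Data regarding predictors of adherence to diabetes medication is limited in Egypt".

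**The concern.** The protocol names determinants of adherence other than beliefs and measures several of them, but never says how they enter the analysis of beliefs and adherence. In a cross-sectional study without matching, a belief score that merely tracks education or treatment burden would look the same in the planned tests as one with its own link to adherence.

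What is at stake is interpretation. A crude association is a weak basis for treating a belief as something to intervene on, and that is the use the hypothesis paragraph looks ahead to. The data needed to check the point for the collected factors will already be in hand.

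**Working it through.** **1. Sample size.** Inputs from Sample size estimation: p = 0.555, precision 0.05, 95% confidence, design effect 1, 10% added for non-response.

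n = 1.96² × 0.555 × 0.445 / 0.05² = 379.5. Then 379 × 1.10 = 416.9, which gives the stated 417. The number was set for the precision of a prevalence, not for tests of association.

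For the analysed number I use 417 × 0.9 = 375. Using 417 / 1.1 = 379 instead changes the rates below by less than 0.5 percentage points.

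**2. How often a shared factor alone makes the crude test significant.** All correlations here are assumed. Let one collected factor correlate a with the belief score and b with adherence, with no link between the two given that factor. The crude correlation is then r = a × b. By Fisher's z, with a two-sided 0.05 test (the plan does not state sidedness):

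m = atanh(r) × √(n − 3); rejection rate = Φ(m − 1.96) + Φ(−m − 1.96).

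Example, a = b = 0.3, n = 375: r = 0.09, m = 0.0902 × √372 = 1.741, rate = 0.413.

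| a, b | crude r | n = 375 | n = 417 |
|---|---|---|---|
| 0.1, 0.1 | 0.01 | 5.4% | 5.5% |
| 0.2, 0.2 | 0.04 | 12.1% | 12.9% |
| 0.3, 0.3 | 0.09 | 41.3% | 45.1% |
| 0.4, 0.4 | 0.16 | 87.5% | 90.7% |

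With unequal correlations at n = 375, the rate is 12.1% for 0.1 and 0.4, 34.0% for 0.2 and 0.4, and 64.3% for 0.3 and 0.4.

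**3. Does adjustment remove it?** Simulation with 4,000 runs, n = 375, an outcome of 5.5 + 2 × normal rounded to 0.25 and clipped to 0–8 to mimic the MMAS-8 total, 12 model terms and HC3 robust standard errors:

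| a = b | crude | adjusted |
|---|---|---|
| 0.1 | 5.5% | 4.5% |
| 0.2 | 11.3% | 4.4% |
| 0.3 | 40.1% | 5.0% |
| 0.4 | 85.8% | 4.7% |

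With adherence split into 55.5% non-adherent and the rest (2,000 runs, n = 379), the pattern is the same. The crude t-test rejects in 9.6%, 28.7% and 72.2% of runs at 0.2, 0.3 and 0.4, and logistic regression adjusted for the factor in about 6% throughout.

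**4. Can the sample carry the model?**

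- Terms: 3 scores + age 1 + sex 1 + education 3 (four levels assumed) + residence 1 + duration 1 + medicines 1 + comorbidities 1 = 12. Patients per term: 375 / 12 = 31.
- Correlation detectable with 80% power: tanh((1.960 + 0.842) / √(375 − 3 − k)). For k = 0 this is 0.144; for k = 11 other terms it is 0.146.
- Precision: if the covariates explain a share R² of a score, its standard error is multiplied by √(1 / (1 − R²)). For R² = 0.1, 0.2 and 0.3 (assumed) this gives 1.05, 1.12 and 1.20. It ignores the outcome variance that the covariates remove. In simulation with one confounder the rise was about 3% to 5%.

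**5. Should the three scores adjust for each other?** Suppose illness perception acts only through a medicine belief, with both links at 0.3 (or 0.4). Its coefficient is then significant in 41% (87%) of runs without the belief score in the model and in 6% (5%) with it. Both versions are therefore needed.

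**The case against.** The strongest reply is that nothing stated fails. The study is a cross-sectional survey sized for a prevalence. Its objectives and aim speak of links, correlates and association, and crude tests deliver those. The mention of predictors occurs in a sentence about what Egyptian data lack, and the directional phrase is background. Even the sentence on interventions speaks of associated factors. This stands. A reader might infer that the plan contradicts its objectives, or commits the study to reporting independent predictors; the documents support neither.

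It is also fair that the figures are hypothetical. The introduction says the factors influence adherence, but not that they relate to beliefs. At correlations of 0.1 there is practically no problem. A reader might infer from the 41% or 88% that the planned results will be confounded; the figures show only that they could be.

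An adjusted analysis can also grow too large or rest on disputable choices. Complications may be a consequence of adherence or may shape both perception and adherence. Number of medicines may follow from poor control. The protocol does not say how the B-IPQ items combine into a score. These points shape the fix below; they do not remove the gap.

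**Conclusion.** The point holds as a limit on interpretation. The planned tests answer objectives 3 and 4 as worded, but cannot separate a belief's own link with adherence from one that reflects a collected factor such as age, education or number of medicines. That weakens the results as a basis for interventions.

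The omission is certain from the text; its consequence is not. Under the assumptions above (one shared factor, no other link, two-sided 0.05, 375 analysed), the problem is negligible at correlations of 0.1 and large from 0.3. It is worth correcting because the correction is cheap. A reader might infer that adjustment would establish beliefs as a cause of adherence. It would not: the design is cross-sectional and several named influences are not listed for collection.

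**What to change.** Keep the crude tests and add to the Statistical analysis section:

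- **Main model for objective 3.** One linear regression with robust standard errors of the MMAS-8 total on the B-IPQ score (with the rule for combining its items stated), BMQ-Necessity and BMQ-Concerns, adjusted for age, sex, education, residence, duration of diabetes, number of medicines and number of comorbidities.
- **Single-score versions.** Each of the three scores with the covariates but without the other two, because illness perception may act through medicine beliefs.
- **Two sensitivity analyses.** One omits number of medicines and comorbidities. The first may follow from adherence; the second the introduction lists within illness perception ("comorbid conditions, number of hospital admission, whether it can be controlled or not"). The other adds number of complications. The introduction presents these as downstream of adherence ("thus helping in reduction of microvascular and macrovascular complications"), but in a cross-sectional design whether they are consequence or confounder is a judgement.
- **HbA1c.** Leave it out as a covariate. If it is modelled as an outcome for the stated aim, omit MMAS-8, and omit number of medicines from the main version because it may follow from poor control.
- **Labelling.** Mark all other results as unadjusted. If no adjusted model is run, state that all associations are unadjusted and do not show an independent or causal effect.

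**Cost.** Six runs (1 + 3 + 2), or seven with HbA1c, on data already collected, and a modest loss of precision: standard errors about 3% to 5% higher in the one-confounder simulation, up to about 20% if covariates explain 30% of a score. Missing HbA1c values would shrink the HbA1c model. Influences named in the introduction but not listed for collection ("side effects, cost, availability, accessibility", and family support) stay unadjusted, and reverse causation remains. The fallback costs one sentence.
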